5.4. Risks of Study Procedures

The potential risks to subjects are those associated with an intramuscular injection and of blood drawing.

Intramuscular injections may cause temporary localized redness, pain or tenderness, swelling, bruising, itching, warmth, or induration at the injection site.

Blood sample collection involves transient discomfort and may cause fainting, which is managed by having the subject lie down prior. The blood draw site may bruise, and this can be ameliorated by holding pressure to this site following the blood draw. The sites of blood draw are potential sites of infection, but this risk is made very unlikely by the use of sterile technique.

5.5. Potential Benefits

Individuals who receive this vaccine will likely gain protection against the development of HZ as this is the recommended vaccine for HZ prevention.

6. Investigational Agent /Device/Intervention

6.1. Investigational Agents/Devices/Interventions

6.1.1. Investigational Agent

The investigational agent used in this study is Shingrix®, a zoster vaccine recombinant, adjuvanted, recently approved by the FDA for prevention of herpes zoster (shingles) in adults aged 50 years and older. It is given in two doses (0.5 mL each): at 0 and 2 to 6 months.

Shingrix® will be donated by the manufacturer (GSK, Brentford, United Kingdom). Subsequent storage and transport of vaccine from the site's pharmacy to the vaccination center will strictly follow the most updated conditions specified in the Shingrix® package insert for *Handling and Storage*. Shingrix® will be administered within the labeled indications and within ACIP-recommended windows for administration.

6.1.1.1. Formulation, Packaging, and Labeling

Shingrix® (Zoster Vaccine Recombinant, Adjuvanted) is a sterile suspension for intramuscular injection. The vaccine is supplied as a vial of lyophilized recombinant varicella zoster virus surface glycoprotein E (gE) antigen component, which must be reconstituted at the time of use with the accompanying vial of AS01B adjuvant suspension component. The lyophilized gE antigen component is presented in the form of a sterile white powder. The AS01B adjuvant suspension component is an opalescent, colorless to pale brownish liquid supplied in vials.

The adjuvant suspension component is AS01B which is composed of 3-O-desacyl-4'-monophosphoryl lipid A (MPL) from *Salmonella minnesota* and QS-21, a saponin purified from plant extract *Quillaja saponaria* Molina, combined in a liposomal formulation. The liposomes are composed of dioleoyl phosphatidylcholine (DOPC) and cholesterol in phosphate-buffered saline solution containing disodium phosphate anhydrous, potassium dihydrogen phosphate, sodium chloride, and water for injection.

After reconstitution, each 0.5-mL dose is formulated to contain 50 mcg of the recombinant gE antigen, 50 mcg of MPL, and 50 mcg of QS-21. Each dose also contains 20 mg of sucrose (as stabilizer), 4.385 mg of sodium chloride, 1 mg of DOPC, 0.54 mg of potassium dihydrogen phosphate, 0.25 mg of cholesterol, 0.160 mg of sodium dihydrogen phosphate dihydrate, 0.15 mg of disodium phosphate anhydrous, 0.116 mg of dipotassium phosphate, and 0.08 mg of polysorbate 80. Shingrix® does not contain preservatives. Each dose may also contain residual amounts of host cell proteins ($\leq 3.0\%$) and DNA (≤ 2.1 picograms) from the manufacturing process.

Shingrix® is supplied as 2 components: A single-dose vial of lyophilized gE antigen component (brown cap) and a single-dose vial of adjuvant suspension component (blue-green cap) (packaged without syringes or needles).

6.1.1.2. Dosage, Preparation, and Administration

Shingrix® is prepared by reconstituting the lyophilized varicella zoster virus glycoprotein E (gE) antigen component with the accompanying AS01B adjuvant suspension component. The reconstituted vaccine should be an opalescent, colorless to pale brownish liquid.

Two doses (0.5 mL each) administered intramuscularly according to the following schedule: A first dose at Month 0 followed by a second dose administered anytime between 2 and 6 months later. The preferred site for intramuscular injection is the deltoid region of the upper arm.

Storage before Reconstitution:

Adjuvant suspension component vials: Store refrigerated between 2° and 8°C (36° and 46°F). Protect vials from light. Do not freeze. Discard if the adjuvant suspension has been frozen.

Lyophilized gE antigen component vials: Store refrigerated between 2° and 8°C (36° and 46°F). Protect vials from light. Do not freeze. Discard if the antigen component has been frozen.

Storage after Reconstitution:

After reconstitution, administer Shingrix® immediately or store refrigerated between 2° and 8°C (36° and 46°F) and use within 6 hours. Discard reconstituted vaccine if not used within 6 hours. Do not freeze. Discard if the vaccine has been frozen.

6.2. Drug Accountability

Under Title 21 of the Code of Federal Regulations (21CFR §312.62) the investigator will maintain adequate records of the disposition of the investigational agent, including the date and quantity of the drug received, to whom the drug was dispensed (participant-by-participant accounting), and a detailed accounting of any drug accidentally or deliberately destroyed.

Records for receipt, storage, use, and disposition will be maintained by the study site investigational drug services. A drug-dispensing log will be kept current for each participant. This log will contain the identification of each participant and the date and quantity of drug dispensed.

All records regarding the disposition of the investigational product will be available for inspection.

All unused vaccine will be destroyed by the Emory Investigational Drug Service according to the pharmacy SOP.

6.3. Assessment of Participant Compliance with Investigational Agent

Not applicable.

6.4. Toxicity Prevention and Management

Unless the vaccine used in the study is recalled by the manufacturer, there will be no modification for the study vaccine during the study.

6.5. Premature Discontinuation of Investigational Agent

Study therapy may be prematurely discontinued for any participant for any of the following reasons:

- Inability to obtain the subject's blood on multiple occasions.
- Subject does not meet the eligibility criteria anymore.
- Development of an anaphylactic or severe allergic reaction after administration of the first study vaccine.

Study therapy may also be prematurely discontinued for any participant if the investigator believes that the study treatment is no longer in the best interest of the participant.

7. Other Medications

7.1. Concomitant Medications

7.1.1. Protocol-mandated

Not applicable.

7.1.2. Other permitted concomitant medications

Subjects are allowed to use acetaminophen or nonsteroidal anti-inflammatory drugs (NSAIDs) if they experience a moderate to severe local or systemic side effects after vaccine administration.

7.2. Prophylactic Medications

Not applicable.

7.3. Prohibited Medications

In accordance with exclusion criteria, subjects expected to receive prohibited medications (see Section 4.3) will be considered non-eligible for the study. All medications, therapies or vaccines administered to study subjects after study entry will be documented at each visit.

7.4. Rescue Medications

Should an anaphylactic or hypersensitivity reaction occur, epinephrine (1:1000) and diphenhydramine intramuscular injections are readily available at clinic sites. If needed, the site will initiate emergency procedures as per their institution policy. If needed, participant will be transferred to the Emory University Hospital Emergency Department.

8. Study Procedures

Shingrix® vaccine will be administered in two doses (0.5 mL each, at D0 and D60) intramuscularly in the deltoid region of the arm. Aseptic technique will be used.

Blood will be drawn at D0 (pre-vaccination), and at D1, D3, D7, D14, D30, D60, D61, D63, D67, D74, D90 D180 and optional D270+ post vaccination. Stool will be collected at baseline D0 (pre-vaccination).

A targeted physical examination will be performed when deemed necessary.

A memory aid will be completed for symptom assessment (local and systemic) from Day 0 to Day 7 and from D60 to D67.

8.1. Enrollment

The research study will be explained in lay terms to each potential research participant. The potential participant will sign an informed consent form before undergoing any study procedures. Once the informed consent has been signed, the participant is considered enrolled in the study and will be assigned a unique participant number.

Enrollment will be completed within 18 months. The duration of participation for each subject is 6 months, with an optional visit at 9 months and beyond after the first visit.

8.2. Screening Visit (D -28 to 0) (Optional Visit)

The purpose of the screening period is to confirm eligibility to continue in the study. The screening visit will last around 1 – 1 1/2 hours.

The following procedures and assessments will be conducted to determine participant eligibility:

1. Collect demographic information
2. Assess inclusion/exclusion criteria
3. Collect medical history, current medications and vaccination history
4. Record vital signs
5. Targeted physical examination if needed based on symptomatology and medical history
6. Provide subject with stool collection kit and instructions and collect stool if possible

8.3. Vaccination Visit (D0 - first dose of vaccination)

The purpose of the screening period is to confirm eligibility to continue in the study.

The following procedures and assessments will be conducted to determine participant eligibility:

1. Review inclusion/exclusion criteria
2. Review medical history, current medications and vaccination history
3. Record vital signs
4. Targeted physical examination if needed based on symptomatology and medical history
5. Draw blood tubes for analysis (pre-vaccination) and collect stool.
6. Administer first dose of Shingrix vaccine (0.5 mL) intramuscularly in the deltoid region of the preferred arm. Aseptic technique will be used.
7. Observe subjects for at least 15 minutes for any immediate hypersensitivity reactions.
8. Record vaccination in the Georgia Registry of Immunization Transactions and Services (GRITS).
9. Provide subjects with memory aid and other study related materials (thermometer and ruler to measure the size of any localized reactions that may occur) to record daily temperature and potential systemic and local side effects.

The visit will last around 1 ½ to 2 hours. No randomization is performed since all subjects, if eligible and wish to proceed with the study, will receive the first dose of the Shingrix® vaccine.

The Screening and Vaccination Visits may be combined into one visit if all activities can be completed in one visit. The combined screening/baseline visit will last around 2 – 2 ½ hours.

Subjects will be encouraged to take their oral temperature around the same time each day. Subjects will be instructed on how to use the memory aid and how to measure and record reactogenicity prior to leaving the clinic. Subjects will be instructed to notify the study center by telephone if they develop any severe reactions following vaccination. If the investigator deems the reaction severe enough, she/he will give further instructions on the proper course of action, including a return to the clinic for immediate evaluation if appropriate.

8.4. Study Visits or Study Assessments

8.4.1. Scheduled Study Follow-up Visits

All subjects will return for follow-up visits on D1, D3, D7 (+/-1), D14 (+/-2), D30 (+/-7), D60 (second dose of vaccine), D61, D63, D67 (+/-1 from second vaccination), D74 (+/-2 from second vaccination), D90 (+/-7 from second vaccination), D180 (+/-14 from first vaccination), and an optional visit past 9 months (D270 +) from first vaccination. These visits will last 30 minutes.

At these visits, study personnel will:

1. Review current health status
2. Record change in medications or receipt of other vaccination (on optional later visit).
3. Note any health changes since last visit
4. Perform a physical examination and vital signs (only if indicated, based on review of health status).
5. Draw blood tubes for analysis
6. Ask subjects to report local and systemic AEs developing the day of any blood draw.
7. Inquire about SAEs.
8. Review memory aid information with subject and examine the vaccine site (on Days 1, 3, 7, and Days 61, 63, 67).

8.4.2 Second Vaccination Visit (Day 60)

This visit will take approximately 2 hours. At this visit, study personnel will:

1. Review current health status.
2. Record change in medications.
3. Review eligibility criteria
4. Note any health changes since last visit.
5. Record vital signs
6. Perform a physical examination (only if indicated, based on review of health status).

7. Draw blood tubes for analysis.
8. Ask subjects to report local and systemic AEs developing the day of any blood draw.
9. Inquire about SAEs.
10. Administer second dose of Shingrix® vaccine.
11. Observe subject for at least 15 minutes for any immediate hypersensitivity reactions.
12. Record vaccination in the Georgia Registry of Immunization Transactions and Services (GRITS).
13. Provide subjects with memory aid and other study related materials (thermometer and ruler) to record daily temperature and potential systemic and local side effects.

Subjects will be encouraged to take their temperature around the same time each day. Subjects will be instructed on how to use the memory aid and how to measure and record reactogenicity prior to leaving the clinic. Subjects will be instructed to notify the study center by telephone if they develop any severe reactions following vaccination. If the investigator deems the reaction severe enough, she/he will give further instructions on the proper course of action, including a return to the clinic for immediate evaluation if appropriate.

8.5. Unscheduled Visits

If concerns arise between regularly scheduled visits, participants should be instructed to contact study personnel and may be asked to return to the study site for an “unscheduled” visit.

Subjects may also be asked to return for an unscheduled visit if phlebotomy is unsuccessful or if insufficient blood is collected at a prior visit. At this visit, study personnel may review their memory aid, review the vaccination site if within 14 days of vaccination, list of medications, and note any other AEs or SAEs since last visit. Blood may be drawn. Physical examination will be performed only if indicated, based on review of health status. Subjects may be also asked to report local and systemic AEs and any blood draw-related AEs or SAEs. These visits will last about 1 hour.

Early Termination Visit

At this visit, study personnel may review the memory aid with the subject (if within 7 days of vaccination) review the vaccination site, list of medications, and note any other AEs or SAEs since last visit. Blood may be drawn. Physical examination will be performed only if indicated, based on review of health status. Subjects will be also asked to report local and systemic AEs and any blood draw-related AEs. These visits will last about 1 hour.

Missed Vaccination Visit

Subjects that may have missed the second dose of the study vaccine due to the COVID-19 pandemic, may be asked to return for missed vaccination visit, if they have not received the second dose from an outside source. Subjects that agree to return will be reconsented. During the missed vaccination visit the same procedures and assessments will be followed as outlined for the second vaccination visit at Day 60. Following the second vaccination the subject will return for regular follow up visits scheduled within the specified time limits.

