8.6. Visit Windows

Study visits should take place within the time limits specified below:

D0 (first dose of vaccination) D1, D3, D7 (+/-1), D14 (+/-2), D30 (+/-7), D60 (+7) (second dose of vaccine), D61, D63, D67 (+/-1 from second vaccination), D74 (+/-2 from second vaccination), D90 (+/-7 from second vaccination), D180 (+/-14 from first vaccination, for each scheduled visit. An optional visit at any time point past 9 months (D270 +) from first vaccination may also take place.

This is also indicated on the Table of Events.

9. Mechanistic Assays

1. Expression of cytokines and chemokines via FACS. This assay will detect the expression profile of cytokines and chemokines to determine the innate response to vaccination.
2. Analysis of innate immune responses using FACS to assess numbers of activated innate cell populations. This assay will detect innate cell population activation including DC subsets, monocyte subsets, and NK cells, since these cell subsets are known to play crucial roles in immune regulation.
3. Molecular signatures of vaccination using RNA-seq on 2 mL of whole blood. This assay will determine the changes in mRNA and miRNA expression in whole blood. Results will be interpreted with use the method Significance Analysis of Microarrays (SAM) to determine change over baseline.
4. Microbiome Analysis: Analysis of microbiome diversity in the stool samples will be performed by Illumina MiSeq V4 16S Sequencing. Sample preparation will involve quantification and normalization of genomic DNA, PCR amplification of V4 hypervariable region of the bacterial 16S rDNA gene, PCR product quantification and library construction. Illumina MiSeq V4 16S sequencing and Bioinformatics analysis will involve V4 hypervariable region paired-end amplicon sequencing (MiSeq: 2x250 cycles). Filtering and trimming of all sequencing data will be done and mapped to taxonomic databases to identify bacterial composition in samples.
5. Levels of VZV-specific IgG/IgA/IgM antibody titers in the plasma by ELISA. This antibody assay will be used to quantify the levels of VZV-specific IgG and IgA in the plasma. Positive results will be assessed by 2X the negative control wells.
6. Number of VZV-specific IgG/IgA/IgM plasmablasts via ELISPOT. This cellular assay will be used to quantify the number of VZV-specific and total IgG/IgA/IgM antibody secreting cells in the blood. Positive results will be assessed by > 5 spots per million PBMCs.

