13.4.1 Analysis Populations

We will use all subjects who receive at least the first dose of the vaccine, and have measurements at days 0 and day 30 after the vaccination in the data analysis.

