13.4.5 Analyses of Exploratory Endpoint(s)/Outcome(s)

Exploratory Endpoint 1. The innate immune response signatures are identified from traditional immune parameters, gene expression measured by RNA-seq experiment, and metabolomics data measured by LC/MS. The innate signatures will be identified for the two age groups separately. The traditional immune parameters, genes, and metabolites that change significantly over baseline after immunization are considered innate signatures.

Traditional markers will be tested using paired t-test or Wilcoxon test against D0, and significant markers will be considered part of the innate immune signature.

RNA-seq data will be preprocessed using Bowtie and Tophat, and FPKM (fragments per kilobase of exon model per million mapped reads) values will be calculated. Gene level comparison of D1, D4, D14 and D30 vs D0 will be conducted using DESeq to find the transcriptomics signature of vaccination.

Metabolomics data will be processed using packages apLCMS, XCMS, and xMSAnalyzer and generate data tables containing accurate mass m/z , retention time(s), intensity, coefficient of variation, and

related descriptive characteristics, including minimal information standards for metabolomics data. SAM(8) and similar methods will be used to detect differential abundance of features between D1, D4, D14 and D30 vs D0 to select metabolic innate signatures.

After each vaccination, the innate signatures that are correlated with the D30 antibody titers are considered correlation signatures of the innate immune responses. The correlation will be assessed using Spearman's correlation and the associated p-values.

Exploratory Endpoint 2. We will use paired t-test or Wilcoxon test to compare each immune parameter (changes in phenotype of T cell responses and the kinetics of these changes) between D7, D14 and D30 after vaccination and D0 for each dose of Zoster vaccine.

Exploratory Endpoint 3. We will use paired t-test or Wilcoxon test to compare each immune parameter (changes in the magnitude of activated B cells, antibody secreting cells and memory B cells and the kinetics of these changes) between D7, D14 and D30 after vaccination and D0 for each dose of Zoster vaccine.

Exploratory Endpoint 4. We will use paired t-test or Wilcoxon test to compare VZV serology between D14, D30, D180 and D270+ (optional visit) after vaccination and D0 for each dose of Zoster vaccine.

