APPENDIX D. SCHEDULE OF EVENTS

Day	D -28 - D0	D0	D1	D3	D7 +/- 1	D14 +/- 2	D3 0 +/- 7	D60 + 7	D61	D63	D67 +/- 1*	D74 +/- 2*	D90 +/- 7*	D18 0+/- 14**	D27 0+** ***
Visit	Screen -ing	1	2	3	4	5	6	7	8	9	10	11	12	13	14
Informed Consent & HIPPA***	X														
Verify Eligibility Criteria	X	X						X							
PID assignment	X														
Demographic and Medical History (including medication and vaccine history).	X	X	X	X	X	X	X	X	X	X	X	X	X	X	X
Concomitant Medications	X%	X%	X	X	X	X	X	X	X	X	X	X	X	X	X
Vital signs (Oral Temperature, Pulse Rate, and BP)	X	X	(X)	(X)	(X)	(X)	(X)	X	(X)	(X)	(X)	(X)	(X)	(X)	(X)
Height and Weight	X														
Focused physical exam (only if indicated based on review of health status)	X	X	X	X	X	X	X	X	X	X	X	X	X	X	X
Vaccination		X						X							
Assessment of health status 15 minutes after administration of study vaccine		X						X							
Memory Aid Review			X	X	X				X	X	X				
Instruction given to study subjects on safety events and concomitant medications****		X	X	X	X	X	X	X	X	X	X	X	X	X	
Blood draw for Innate Assays and Adaptive Assays		X	X	X	X	X	X	X	X	X	X	X	X	X	X
Stool collection	X	X													
Adverse Events		X	X	X	X	X	X		X	X	X	X	X	X	
Serious Adverse Events		X	X	X	X	X	X	X	X	X	X	X	X	X	X

Footnotes:

%All current medications and medications taken within 30 days prior to day 0 of the study.

* Windows here are in relation to the second (D60) vaccination: D67 (+/-1 from second vaccination), D74 (+/-2 from second vaccination) and D90 (+/-7 from second vaccination).

** D180 +/- 14 days from first vaccination,

***Prior to study procedures

*****D270+, an optional visit at 9 months and beyond, after the first visit may occur.

Any Adverse Event (including – but not limited to- vaccine reactions and local or systemic reactogenicity events) of grade 2 or higher severity or serious adverse event (SAE) occurring after vaccination while the subject is still at the clinical site will be recorded and reported.

**** Instruction includes the following:

1. Subjects will be provided (on D0 and D60 only) with a written description of local and systemic vaccine reactions of mild, moderate and severe intensity and instructed to call the site to report reactogenicity events of grade 3 severity within 1 week following vaccination.

2. Subjects will also be instructed to promptly call the site if he/she develops any of the following:

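### After a COVID-delayed dose 2, D180 and D270+ stay dated from dose 1, so exploratory tests 4 to 6 pool different times since dose 2 and no analysis separates them

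*Combined protocol and SAP*

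**What the plan says.** - **Late dose 2.** The Missed Vaccination Visit in section 8.5 covers participants who missed dose 2 because of the pandemic and have not had it elsewhere. They are reconsented and go through the Day 60 procedures. Then: "Following the second vaccination the subject will return for regular follow up visits scheduled within the specified time limits". No longest permitted delay is given there. Section 6.1.1.2 describes the vaccine schedule as a first dose "followed by a second dose administered anytime between 2 and 6 months later".
- **Two clocks.** For D67, D74 and D90, the Appendix D footnote says "Windows here are in relation to the second (D60) vaccination". For the later visit, section 8.6 has "D180 (+/-14 from first vaccination" and Appendix D repeats "D180 +/- 14 days from first vaccination". Sections 8.4.1 and 8.6 also count the optional D270+ visit from the first vaccination.
- **Who is analysed.** Section 13.4.1 takes "all subjects who receive at least the first dose of the vaccine" and who have D0 and D30 measurements. Receipt or timing of dose 2 plays no part.
- **Which tests.** For exploratory endpoint 4, section 13.4.5 plans a paired t-test or Wilcoxon test to "compare VZV serology between D14, D30, D180 and D270+ (optional visit) after vaccination and D0". Endpoints 5 and 6 (VZV-specific T cells and B cells) name D180 and D270+ in the same way.

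**The concern.** When dose 2 is given on D60 to D67, the two clocks run nearly in step: D180 means about six months after dose 1 and about four months after dose 2. The missed-vaccination pathway breaks that link. A delayed participant keeps the D180 date set by dose 1, so the sample may come only weeks after dose 2, or before it. Nothing in the plan moves the visit, sets such participants apart, or accounts for days since dose 2.

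D180 is the last visit that is not optional, so readers will take it as the main view of how long the response lasts after the two-dose course. A value that blends four months after dose 2 with one month after it cannot be read that way. Participants who never receive dose 2 enter the same contrast, and for them D180 is a one-dose result.

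The same pathway may reach the primary analysis. The Day 60 procedures (8.4.2) include a blood draw, listed before the vaccination. If that draw, taken late, is labelled D60, a D0-versus-D60 comparison (13.4.2) would mix different times since dose 1.

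**Working it through.** **Inputs from the protocol.** Dose 2 on schedule: D60 (+7), so day 60 to 67 (8.6). D180 window: 180 ± 14, so day 166 to 194 from dose 1 (8.6, Appendix D). Visit 30 days after dose 2, labelled D90: 30 ± 7, so 23 to 37 days after dose 2. Planning figure: paired t-test, n = 30, two-sided alpha 0.01, effect size 0.66, 80% power (13.7).

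**Assumptions.** The delayed dose-2 days below are examples, because the documents give neither the number of delayed participants nor the length of the delays. Six months is taken as 183 days.

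**1. The plan's own figure.** Noncentral t, 29 degrees of freedom, noncentrality 0.66 × √30: power is 79.7%. The smallest effect with 80% power is 0.662. The stated 0.66 reproduces.

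**2. Time since dose 2 at D180.** With dose 2 on day d, the interval runs from 166 − d to 194 − d.

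| Dose 2 on day | Days since dose 2 at D180 |
|---|---|
| 60 to 67 (on schedule) | 166 − 67 = 99 to 194 − 60 = 134 |
| 90 | 76 to 104 |
| 120 | 46 to 74 |
| 150 | 16 to 44 |
| 183 (end of the six-month range) | −17 to 11 |

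**3. Where the label stops meaning the same thing.**
- No in-window sample reaches the on-schedule range once 194 − d < 99, so from d = 96. That is 96 − 67 = 29 days past the end of the D60 window.
- The whole window of the 30-day post-dose-2 visit lies inside the D180 window when d + 23 ≥ 166 and d + 37 ≤ 194, so for d = 143 to 157. The two visits then cover the same stretch of time.
- An in-window D180 sample can precede dose 2 once 166 − d < 0, so from d = 167. The whole window precedes dose 2 once 194 − d < 0, so from d = 195, which is beyond the six-month range.

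**4. D270+.** At its earliest day, 270, time since dose 2 is 270 − 67 = 203 to 270 − 60 = 210 days on schedule, 150 days for d = 120 and 120 days for d = 150. The visit is open-ended, so its interval varies even without delay; a late dose 2 widens the spread at the short end.

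**5. D60 sample.** On schedule it is taken 60 to 67 days after dose 1. A pre-dose draw at a missed-vaccination visit on D120 or D150 would be 120 or 150 days after dose 1.

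**6. Precision of a restricted analysis.** Same test, alpha and power as in step 1: the detectable effect is 0.66 at n = 30, 0.70 at n = 27 and 0.75 at n = 24. The last two counts are illustrative.

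**The case against.** The strongest reply is that D180 is not mis-specified. The protocol consistently dates it from dose 1, and the paired test against D0 asks whether responses have changed about six months after vaccination began. That stands. A reader might infer that the D180 tests are invalid; the documents do not support this. What is missing is any way to read the same data by time since dose 2.

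A second reply is that section 13.4.5 already allows alternative approaches ad hoc, for endpoints that are only exploratory. This is a reason to rate the point as minor. It does not supply the analysis, and a subset chosen after the data are seen carries less weight than one fixed in advance.

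A third is that nobody may have been delayed, and that any delay may have stayed within six months. Both are possible. Section 8.5 states no limit of its own, and section 6.1.1.2 could be read as one. Step 2 shows that the spread is wide even under that cap.

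Two further inferences go too far. One is that the results are biased upward because late participants are sampled closer to dose 2. A sample taken before dose 2 could pull the other way, and the documents give no response ratio from which to calculate a shift. The other is that the primary analysis is definitely affected. Section 13.4.2 can be read as a direct D0-versus-D60 comparison, or as using D60 as the baseline for D61 and D67. On the second reading a late pre-dose draw is the right baseline. The documents also do not say whether a late draw would replace the D60 sample. It would be equally unsupported to say that only D180 is affected, since D270+ is tested in the same endpoints and shares its anchor.

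**Conclusion.** The point holds and is minor. As written, the D180 and D270+ contrasts in exploratory endpoints 4 to 6 would pool participants whose time since dose 2 may differ by months, together with any who had no dose 2, and no planned analysis separates them. The day counts follow from the stated windows; only the delayed dose-2 days are assumed. The effect on results cannot be sized: the number delayed is not given and may be zero, and neither the direction nor the amount of any shift is known. The primary D0-versus-D60 comparison is touched only if it is a direct contrast and late pre-dose draws are used as the D60 sample; the plan should settle both.

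**What to change.** Add a short paragraph to section 13.4:

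- Keep the all-participant contrasts as planned.
- Prespecify a sensitivity analysis of D180 and D270+ versus D0, for exploratory endpoints 4 to 6, restricted to participants with dose 2 on D60 to D67.
- State whether a pre-dose draw at a missed-vaccination visit counts as the D60 sample. If it does, apply the same restriction to D0 versus D60.
- Show delayed participants by actual days since dose 2. List those without dose 2 as a separate dose-1-only group, since no such interval exists for them.
- Show participants with an outside-source dose by days since dose 2 only where the date is documented.

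For study-given doses no new data are needed: the dispensing log in section 6.2 holds "the identification of each participant and the date and quantity of drug dispensed". That log does not cover outside-source doses. Section 7.3 has vaccines received after entry documented at each visit but does not expressly promise dates.

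The cost is a few lines of text and the lower precision of the restricted analysis shown in step 6. The all-participant contrasts lose nothing.
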